9.4.1	Primary outcome.....	Error! Bookmark not defined.
9.4.2	Secondary outcomes	Error! Bookmark not defined.
9.5	Data Analyses	22
10	DATA COLLECTION AND QUALITY ASSURANCE	23
10.1	Data Collection Forms	23
10.2	Data Management	24
10.3	Quality Assurance.....	24
10.3.1	Training.....	24
10.3.2	Quality Control Committee.....	24
10.3.3	Metrics	24

10.3.4	Protocol Deviations.....	24
10.3.5	Monitoring	25
11	PARTICIPANT RIGHTS AND CONFIDENTIALITY	25
11.1	Institutional Review Board (IRB) Review.....	25
11.2	Informed Consent Forms	25
11.3	Participant Confidentiality	25
11.4	Study Discontinuation.....	26
12	ETHICAL CONSIDERATIONS.....	26
13	COMMITTEES.....	27
14	PUBLICATION OF RESEARCH FINDINGS	27
15	REFERENCES.....	27
16	SUPPLEMENTS/APPENDICES	29

I. Procedures Schedule

II. Informed Consent Form Template

III. Other (*add as many appendices as necessary*)

PRÉCIS

Study Title

Therapeutic Intervention Supporting Development from NICU to 6 months for Infants Post Hypoxic-Ischemic Encephalopathy

Objectives

Primary Objective: Feasibility Aims

1. Is it feasible to complete 1 baseline survey, 1 assessment and 2 parent/therapist collaborative sensorimotor intervention (SMI) sessions with infants with moderate or severe hypoxic-ischemic encephalopathy (HIE) or neonatal encephalopathy (NE) prior to discharge from the Newborn and Infant Critical Care Unit (NICCU)?
2. What proportion of parents complete $\geq 80\%$ of the recommended SMI intervention?
3. What proportion of parents complete 100% of the baseline survey and 3 assessment visits?

Secondary Objectives

4. Is it feasible to evaluate the impact of brain lesion location on response to the SMI intervention?

Design and Outcomes

The purpose of this clinical trial (CT) is to evaluate the feasibility and begin to evaluate the effect of early sensorimotor intervention (SMI) for infants with HIE or NE. Twenty infants with HIE or NE and their parent will receive the therapeutic intervention that is typically provided in the NICCU and community (standard care), but infants in this study will receive an additional 2 SMI intervention sessions in the Children's Hospital of Los Angeles (CHLA) NICCU and 8 SMI intervention sessions in the home, at CHLA or at the University of Southern California (USC) Health Sciences Campus over the first 6 months of life. They can also occur via telehealth. These 10 sessions will consist of supporting parents to provide their infants with **daily** opportunities for positive sensory experiences and therapeutic play to enhance development.

- To determine feasibility (Aim 1 and 2), timing and participation in the SMI intervention sessions will be reported.
- To assess fidelity and adherence (Aim 2), parents will be asked to complete a log of their child's activities one day per week, randomly selected, for the 26 weeks from baseline to the end of intervention.
- To assess fidelity of the assessment schedule (Aim 3), parents will be asked to participate in developmental assessments at baseline, NICCU discharge, 3 months of age and 6 months of age. The assessments will include: Test of Infant Motor Performance at NICCU discharge and 3 months of age; the Bayley Scales of Infant and Toddler Development 4th edition at 6 months of age; and the Maternal Confidence Questionnaire, Parenting Stress Index, and Sensory Profile 2 at baseline and/or NICCU discharge, and 3 and 6 months of age.
- To characterize the participants (Aim 4), infants will have medical and

sociodemographic data collected from parents and electronic medical records, including the discharge summary from the NICCU, brain imaging, neurology reports, and reports from the High-Risk Follow Up Clinic. Parents will also be asked to self-report medical needs between assessment visits, use of daycare, and access to community therapy services using standardized questionnaires.

- To identify infants at high risk of cerebral palsy (Aim 4), infants will be assessed using Prechtl's General Movement Assessment at NICCU discharge and at 3 months and using the Hammersmith Infant Neurological Exam at 3 and 6 months of age.
- To assess the feasibility of evaluating the impact of brain lesion location on response to intervention (Aim 4), data from the magnetic resonance imaging (MRI) scan that is provided to all infants with HIE post therapeutic hypothermia or NE at CHLA will be analyzed to characterize the degree of HIE brain injury or NE and involvement of specific motor regions of the brain.

Interventions and Duration

All infants will receive the therapeutic intervention that is typically provided (standard care) in the CHLA NICCU and community, and infants in this trial will receive an additional 2 SMI intervention sessions in the CHLA NICCU and 8 SMI intervention sessions in the home, at CHLA, or at the University of Southern California (USC) Health Sciences Campus over the first 6 months of life at 1, 3, 5, 8, 11, 15, 20, 26 weeks post NICCU discharge. They can also occur via telehealth. If the infant is referred by a local NICU, they will omit the 2 SMI intervention in at CHLA. These 10 1-hour sessions will be provided by a licensed physical or occupational therapist and will consist of supporting parents to provide their infants with daily opportunities for positive sensory experiences and therapeutic play to enhance development. If the infant is at CHLA at 2 weeks after therapeutic hypothermia, the sessions can be done at CHLA or via telehealth until the child is discharged home.

Sample Size and Population

Twenty infants with HIE or NE and their parents (dyad) will participate in this clinical trial.

STUDY TEAM ROSTER

Principal Investigator: [name], PT, FAPTA

[name]

[contact]

[contact]

Main responsibilities/Key roles: coordinating and ensuring progress of the entire study with a focus on the intervention team

Co-Investigator/ MPI on grant: [name], PT – listed on ceded USC IRB

[name]

[contact]

[contact]

Main responsibilities/Key roles: coordinating and ensuring progress of the entire study with a focus on the assessment team

Co-Investigator: [name], OTR/L, CNT

[name]

[contact]

Main responsibilities/Key roles: coordinating the two intervention sessions in the CHLA NICCU; collecting parent-report outcome measures during the NICCU stay

Co-Investigator: [name], PT, DPT, PhD

[name]

[contact]

Main responsibilities/Key roles: analyzing parent report data

1 STUDY OBJECTIVES

1.1 Primary Objective

Primary Objective: Feasibility Aims

1. Is it feasible to complete 1 baseline survey, 1 assessment and 2 parent/therapist collaborative SMI intervention sessions with infants with moderate or severe HIE or NE prior to NICCU discharge?
H1: $\geq 80\%$ of eligible infants will enroll and complete 1 baseline survey, 1 assessment and 2 intervention visits.
2. What proportion of parents complete $\geq 80\%$ of the recommended SMI intervention?
H2a: Parent/infant dyads will complete at least 8 of 10 recommended visits with the therapist.
H2b: Parents will report daily completion of interventions on 80% of randomly sampled days.
3. What proportion of parents complete 100% of the baseline and 3 assessment visits?
H3a: Parent/infant dyads will complete the baseline and 3 assessment visits.

Secondary Objectives

4. Is it feasible to evaluate the impact of brain lesion location on response to intervention?
H4: $\geq 50\%$ of enrolled infants will have an MRI with tractography and cortical volume measurement post therapeutic hypothermia.

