4 SELECTION AND ENROLLMENT OF PARTICIPANTS

4.1 Inclusion Criteria

To be eligible to participate, an individual must meet all of the following criteria:

1. One adult parent/legal guardian has provided signed and dated informed consent form agreeing to the child's participation and the parent's own participation. If a parent/legal guardian is providing consent for a child's participation and a different adult caregiver will be participating, the other adult caregiver must consent to their own participation
 - a. A parent/legal guardian must be willing to also be enrolled in the study and be legally able to consent to their own participation in the research (18 years or over). Parents/legal guardians who are under 18 years and remain in the care of their parents are likely to have a different level of caregiving and support than those who are adults which may impact the delivery of the intervention and assessment visits. If one parent is over 18 years, that parent can participate.
 - b. Inclusion criteria for the adult is that they will be a caregiver for the enrolled infant
 - c. Stated willingness to comply with all study procedures and availability for the duration of the study
2. Infants with HIE based on the modified Sarnat Exam on admission¹⁷ and has started to receive therapeutic hypothermia for 72 hours.¹⁸ Or infants with neonatal encephalopathy.
3. Cared for in the Newborn and Infant Critical Care Unit (NICCU) at Children's Hospital Los Angeles (CHLA) or by referral from other local NICUs.
4. Family lives within 60 miles of CHLA.

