4.3 Study Enrollment Procedures

- The medical records of all infants with HIE or NE at the CHLA NICCU will be screened for eligibility, i.e. searching for infants who had a diagnostic/ICD-10 code associated with HIE, including neonatal encephalopathy, birth depression, intrapartum asphyxia.
- Parents of eligible infants will be taken to a private space, provided information about the study, and asked to consent to the study. Documentation of reasons for ineligibility and for non-participation of eligible candidates will be completed using a screening log in REDCap.
- Once consented, infants will receive standard care plus sensorimotor intervention (SMI). If referred by other local NICU, infants will follow the same procedure of consenting within 72 hours of discharge.

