9.2 Sample Size and Randomization

No power analysis is included as this is a pilot study.

Refer to Enrollment, Baseline, and/or Randomization on page 11 for details on enrollment.

The assessors will not discuss intervention with the interventionist. Some assessments will be videotaped and scored via video by coders.

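### H1 and H2a make no allowance for the two NICCU sessions that referred infants omit: H1 cannot count these infants as successes, and H2a leaves them no missed visit

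*Combined protocol and SAP*

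**What the plan says.** Section 1.1 sets the primary feasibility hypotheses, and section 9.5 repeats them.

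- Aim 1 asks about a baseline survey, an assessment and "2 parent/therapist collaborative SMI intervention sessions with infants with moderate or severe HIE or NE prior to NICCU discharge". Its hypothesis, H1, is that at least 80% "of eligible infants will enroll and complete 1 baseline survey, 1 assessment and 2 intervention visits".
- Aim 2 asks what proportion of parents complete at least 80% of the recommended intervention. H2a reads "Parent/infant dyads will complete at least 8 of 10 recommended visits with the therapist".
- Section 4.1, item 3, admits infants cared for in the CHLA NICCU and also infants referred from other local NICUs.
- The Précis (Interventions and Duration) states: "If the infant is referred by a local NICU, they will omit the 2 SMI intervention in at CHLA". Sections 3 and 5.1 say the same, which leaves eight post-discharge visits.
- Section 5.4 defines non-adherence as attending under 70% of planned sessions.
- On size, the Précis says "Twenty infants with HIE or NE and their parents (dyad) will participate in this clinical trial", and section 9.2 says "No power analysis is included as this is a pilot study".

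For H1 and H2a, section 9.5 adds only that frequencies and proportions will be used. Neither section has an exception or a separate denominator for referred infants.

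**The concern.** A referred infant whose family follows the protocol perfectly has no pre-discharge session to complete, so that infant does not satisfy H1 as Aim 1 frames it. Under H2a the same family must attend every visit offered, while a family recruited in the CHLA NICCU can miss two and still pass. The two primary feasibility proportions then depend partly on how many referrals happen to be enrolled, and not only on whether the programme can be delivered.

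The plan also leaves open whether referred infants belong in the H1 denominator. That choice could be made after the data are seen, and it can move H1 across its 80% mark. These proportions are the main product of a pilot meant to inform a later trial.

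**Working it through.** **Inputs from the documents.** 20 enrolled dyads (Précis); 2 NICCU plus 8 later sessions, 10 in all (Précis, 5.1); H1 threshold 80% of eligible infants and H2a threshold 8 of 10 (1.1). The sample size has no calculation behind it, so there is none to reproduce. The H2a figure agrees with Aim 2 for CHLA dyads: 0.80 × 10 = 8.

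**Inputs assumed.** The number of referrals, r, is not given. The number of eligible infants, E, is not given but is at least 20 once 20 are enrolled. Attendance per visit, p, is taken as independent across visits, at 0.80, 0.90 and 0.95.

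**H1 ceiling, if referred infants are in the denominator.** Suppose every non-referred enrolled infant completes everything. The best possible H1 is (20 − r)/E.

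| r | E = 20 | E = 22 | E = 25 |
|---|---|---|---|
| 0 | 100% | 91% | 80% |
| 2 | 90% | 82% | 72% |
| 3 | 85% | 77% | 68% |
| 4 | 80% | 73% | 64% |
| 5 | 75% | 68% | 60% |

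Reaching 80% needs E ≤ (20 − r)/0.80. For r = 4 that is E ≤ 20, so every eligible infant must enroll and every non-referred infant must complete. For r = 5 it is E ≤ 18.75, which cannot happen with 20 enrolled.

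**H2a for one dyad.** A CHLA dyad passes with at least 8 of 10: 45p⁸(1−p)² + 10p⁹(1−p) + p¹⁰. A referred dyad passes only with 8 of 8: p⁸. Scored at 80% of its own planned visits, a referred dyad needs 0.80 × 8 = 6.4, rounded up to 7 of 8: 8p⁷(1−p) + p⁸.

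| p | CHLA, 8 of 10 | Referred, 8 of 8 (as written) | Referred, 7 of 8 |
|---|---|---|---|
| 0.80 | 0.68 | 0.17 | 0.50 |
| 0.90 | 0.93 | 0.43 | 0.81 |
| 0.95 | 0.99 | 0.66 | 0.94 |

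**A case that shows the conflict.** A referred dyad attends 7 of its 8 visits: 7/8 = 87.5%. That exceeds Aim 2's 80%. It is adherent under 5.4 whether the base is 8 (87.5%) or 10 (70%, which is not below 70%). It still fails H2a, because 7 is less than 8.

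**The case against.** Four stronger conclusions are tempting, and the documents do not support them.

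- *Referred infants cannot meet H2a.* They can: eight visits satisfy a bar of at least eight. H2a also sets no percentage for the cohort, so no number of referrals makes it fail for the trial.
- *Five referrals make H1 impossible.* This holds only if referred infants are in the denominator, and five is an illustration. Section 4.1 uses NICCU for the CHLA unit and contrasts it with other local NICUs, and section 4.3 says "The medical records of all infants with HIE or NE at the CHLA NICCU will be screened for eligibility". On that basis Aim 1 can be read as covering CHLA infants only, and referrals could not lower H1. The H1 sentence itself also leaves out the pre-discharge condition; if any two visits counted, referred infants could pass, though that would not answer Aim 1.
- *Every eligible infant is already enrolled, because 4.1 opens with* "One adult parent/legal guardian has provided signed and dated informed consent form". Sections 4.3 and 6.2.1 use eligible for infants whose parents have yet to be asked, and reasons for non-participation of eligible candidates are logged. The intended meaning is clear.
- *Referred families cannot be counted.* Section 10.1 describes a recruitment database that also takes candidates found by clinicians or parents and records consent. Only infants at other units who were never brought to the study go uncounted.

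It is also fair to say that this is a single-arm pilot with no formal test, that no progression decision is tied to H1 or H2a, and that results could be split by referral source when reported. That lowers the stakes. It does not settle how the stated hypotheses are to be scored, and the 7-of-8 case is a wrong result from a stated rule, not just a missing detail.

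**Conclusion.** The concern stands in limited form and should be fixed. Under Aim 1's wording a referred infant cannot be an H1 success. Whether this lowers H1 depends on a denominator that the plan does not define. If referred infants are included, the ceiling is (20 − r)/E: 80% at four referrals and 75% at five when E = 20, and lower for larger E. H2a is attainable for referred dyads but is a much harder test: 0.17, 0.43 and 0.66 against 0.68, 0.93 and 0.99 at attendance of 0.80, 0.90 and 0.95. Those probabilities rest on assumed, independent attendance. The conflict with Aim 2's own 80%, shown by the dyad attending 7 of 8, needs no assumption.

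**What to change.** Amend sections 1.1 and 9.5.

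1. State that H1 applies to infants cared for in the CHLA NICCU. Take as denominator all screened CHLA infants who meet the 4.1 criteria other than the consent signature and have no 4.2 exclusion, whether or not their parents consented. Keep the limits in items 1a to 1c (adult caregiver aged 18 or over, availability) where they are known; dropping them would count families who could never have joined.
2. Restate H2a as at least 80% of the visits planned for that dyad: 8 of 10, or 7 of 8 if referred. Report it by referral route, and reconcile its base with the planned-sessions base in 5.4.

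The cost is wording in two sections and a referral flag in REDCap. H1 will rest on 20 minus the number of referrals among enrolled infants. With five referrals that is 15, and H1 would need 12 of 15 if all eligible CHLA infants enroll. The revised H2a is not perfectly even, since 7 of 8 (87.5%) is still slightly stricter than 8 of 10: 0.81 against 0.93 at 90% attendance. That is one reason to show the two routes separately.

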2 BACKGROUND AND RATIONALE

2.1 Background on Condition, Disease, or Other Primary Study Focus

Hypoxic-ischemic encephalopathy (HIE) is a form of newborn brain injury due to a lack of oxygen (hypoxia) or blood flow (ischemia) to the brain, which results in a high incidence of moderate-severe disability. Worldwide, HIE is estimated to affect more than 1 million infants born annually.¹ Over 85 percent of infants with HIE now survive to discharge from the Neonatal Intensive Care Unit (NICU).² Currently, therapeutic hypothermia is standard of care, which has improved survival rates but not the incidence of moderate-severe disability or cerebral palsy.³ In a review of 7 major randomized controlled trials of therapeutic hypothermia for HIE, at 18 to 24 months after hypothermia, an average of 26% of children had a major neurodevelopmental impairment (range 14-35%), 25% had a significant cognitive impairment (range 23-30%), and 23% developed cerebral palsy (range 13-32%).⁴ These neurodevelopmental disabilities do not resolve with time as moderate to severe disability at 18 months is highly correlated with outcome at 6-7 years of age.⁵

Study Rationale

A **critical gap** is that there are no clinical trials that have targeted rehabilitation to support infants with HIE prior to the onset of motor delay with the goal of reducing

severity of disability. Therapeutic hypothermia works in the acute phase of brain injury by mitigating secondary energy failure to rescue dying neurons, without a clear role in inducing positive neuroplasticity.⁶ Therefore, infants with HIE may benefit from close developmental surveillance and sensorimotor intervention (SMI) to induce positive neuroplasticity and optimize developmental outcomes. In addition, parents of infants with HIE may benefit from anticipatory guidance to promote global development and extensive education on how to incorporate play-based interaction into their daily routine to induce positive neuroplasticity and optimize developmental outcomes.

In clinical practice, logistical barriers prevent infants with HIE from receiving early developmental intervention. The infants are usually discharged within 3 to 7 days after completing therapeutic hypothermia, so the timeline for assessment of the infant's neurodevelopment and the opportunities for parent training, positive sensory experiences, and anticipatory guidance in the NICU are limited. In addition, while therapeutic intervention provided in the NICU is typically covered by medical insurance, post discharge infants' developmental interventions are generally supported by Early Intervention under the Individuals with Disabilities Education Improvement Act.⁷ However, current policy provides significant barriers to beginning intervention within days of discharge from the NICU leaving parents with limited resources to support development in their infant at high risk of developing cerebral palsy.⁸ A “wait and see” approach is commonly used resulting in delays in referral for assessment or therapeutic intervention until consistent signs of delay are present.⁹ With the wide range of “typical” onset of motor skills, many infants are not referred for intervention until they are not sitting at 9 to 12 months, missing a peak opportunity to prevent delays by intervening early.

Therapeutic intervention provided immediately and consistently after HIE and prior to the onset of developmental delay may prevent or substantially reduce the severity of delay reducing overall cost of care. The proposed intervention blends a therapist-supported, parent-delivered sensorimotor intervention (SMI) that begins in the CHLA NICCU and builds on developmental opportunities once discharged and continuing through the first 6 months of life. The CHLA NICCU phase serves to support the infant and parent in building a relationship, helps to identify ideal times of interaction, and empowers the family to engage in positive sensory experiences with their infant.¹⁰ Once discharged home, training the parent to provide 20 minutes of developmentally appropriate play activities using a variety of strategies to address key principles of the intervention is feasible. Parents describe embedding learned skills into their daily caregiving once they have been supported in their implementation.^{11,12} In contrast, parents without this support report it being difficult to add new routines. Thus, it is critical that intervention starts as early as possible to support the parents' adherence to the intervention principles and dose of intervention while supporting the child's interest in social and cognitive enrichment provided during play.^{13,14}

The SMI is based on two evidence-based approaches: SENSE (Supporting and Enhancing NICU Sensory Experiences)^{10,15} and SPEEDI (Supporting Play, Exploration, and Early Developmental Intervention).¹⁶ While past studies and an ongoing large

clinical trial at 2 sites [PI [name], SMI¹², [NCT03518736](#)] are measuring the efficacy of this type of SMI intervention for infants born preterm, infants with HIE are at high risk of developing cerebral palsy, yet have been excluded from this ongoing work to reduce heterogeneity of the sample. This study addresses this gap in the research literature.

3 STUDY DESIGN

The purpose of this clinical trial (CT) is to evaluate the feasibility and begin to evaluate the effect of early sensorimotor intervention (SMI) for infants with HIE. Twenty infants with HIE and their parent will receive the therapeutic intervention that is typically provided in the CHLA NICCU and community (standard care), but the infants will also receive an additional 2 SMI intervention sessions in the CHLA NICCU (unless referred by local NICU) and 8 SMI intervention sessions in the home, at CHLA, or at the University of Southern California (USC) Health Sciences Campus over the first 6 months of life. They can also occur via telehealth. These 10 sessions will consist of supporting parents to provide their infants with daily opportunities for positive sensory experiences and therapeutic play to enhance development. Infants will be assessed by masked assessors at baseline, at NICCU discharge, and at 3 months and 6 months of age using standardized developmental and neurological assessments, parent-report measures via questionnaires, and medical records.

